## 8.3 Sample Size

The sample size is based on the following assumptions

- Four countries with asymmetrical countrywide enrollments ranging from 15% to 25% of the total enrollment (conservative assumption)
- Standard Deviation = 8.5
- Difference between the lower and upper 2-sided 95% Confidence interval = 2
- 10% of patients missing either baseline or 12 month IPSS

A sample size of up to 500 patients is required to estimate the 12 month change from baseline in the IPSS within +/- 1 unit. Sample size calculations were performed using NCSS PASS 2020's procedure for one mean in a stratified design.

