## 8.5.2 Analysis of the Primary Endpoint

The stratified sample mean change from baseline in 12 month IPSS is estimated as follows.

$$\bar{x} = \sum_{h=1}^L \frac{N_h}{N} \sum_{i=1}^{n_h} \frac{X_{hi}}{n_h} = \sum_{h=1}^L \frac{N_h}{N} \bar{x}_h$$

where  $\bar{x}$  is the stratified sample mean,  $L$  is the number of strata,  $X_{hi}$  is change from baseline in 12 month IPSS for the  $i^{th}$  patient in the  $h^{th}$  stratum,  $N$  is the overall sample size and  $N_h$  is the sample size in stratum  $h$

It can be shown in T. Yahane(1967) that the expected value and variance of  $\bar{x}$  ( $V(\bar{x})$ ) assuming sampling without replacement are

$$E(\bar{x}) = \mu$$

$$V(\bar{x}) = \sum_{h=1}^L \left(\frac{N_h}{N}\right)^2 \left(\frac{N_h - n_h}{N_h n_h}\right) S_h^2$$

$$S_h^2 = \frac{1}{N_h - 1} \sum_{i=1}^{N_h} (X_{hi} - \mu_h)^2$$

where

The 95% confidence interval ( $CI(\mu)$ )s calculated as follows:

$$CI(\mu) = \bar{x} \pm z_{1-\alpha/2} \sqrt{\hat{V}(\bar{x})}$$

where  $\alpha$  is the type I error and  $\hat{V}(\bar{x})$  is the unbiased estimator of  $V(\bar{x})$  and is calculated as follows:

$$\hat{V}(\bar{x}) = \sum_{h=1}^L \left(\frac{N_h}{N}\right)^2 \left(\frac{N_h - n_h}{N_h n_h}\right) S_h^2$$

$$s_h^2 = \frac{1}{n_h - 1} \sum_{i=1}^{n_h} (X_{hi} - \bar{x}_h)^2$$

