### 8.5.2.1 Missing Data

Missing data for the IPSS will be imputed as the age-specific average for that time point. Also, a tipping point analysis will be performed where the analysis will be performed, excluding the missing data. The number of missing data points it takes to tip the results from one direction to the other will be reported.

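### The primary confidence interval uses a finite-population correction with the trial's own sample as the population, so it has zero width after the planned imputation and is about 3.2 times too narrow with 10% missing

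*Combined protocol and SAP*

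**What the plan says.** Section 8.2 sets the primary statistical objective as estimating the 12-month change from baseline in IPSS to within one unit either way. Section 8.3 sizes the trial for that precision: "Difference between the lower and upper 2-sided 95% Confidence interval = 2", with "Standard Deviation = 8.5", "10% of patients missing either baseline or 12 month IPSS" and up to 500 patients in four country strata.

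Section 8.5.2 gives the estimator. The stratified mean weights each country's mean by `N_h/N`. Its expectation and variance are given "assuming sampling without replacement are" a sum over strata of `(N_h/N)² × (N_h − n_h)/(N_h n_h) × S_h²`. The estimated variance has the same form, and the interval is the mean ± z times its square root. On the symbols, the text says that "N$ is the overall sample size and $N_h$ is the sample size in stratum $h". `n_h` is not defined in words. In the formulas it is the number of change scores summed and averaged in stratum h.

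Section 8.5.2.1 adds that "Missing data for the IPSS will be imputed as the age-specific average for that time point". It also plans an analysis that leaves the missing data out.

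**The concern.** The factor `(N_h − n_h)/N_h` belongs to a survey in which `n_h` units are drawn from a known, finite list of `N_h` units and the target is the mean of that list. It removes sampling variance because units already measured need no inference. Here `N_h` is defined as the trial's own stratum sample, so the factor measures how much of the trial is missing. An analyst who follows the text gets a smaller standard error the more completely the same cohort is observed, reaching zero when all values are present.

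The study aims to assess long-term effectiveness in routine practice (section 2), which means inference beyond the patients enrolled. Sampling variance therefore remains even when every enrolled patient has a score.

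The plan attaches no hypothesis test or success threshold to the mean change. The interval is the whole primary result, so an error in its width is an error in the primary result.

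**Working it through.** **Inputs.** SD 8.5, two-sided 95%, target half-width 1, 10% missing, up to 500 patients and four countries (section 8.3). Variance formula and definitions from section 8.5.2. Imputation rule from section 8.5.2.1.

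**The plan's own figure.** Without any correction, the number of patients with data needed for a half-width of 1 is `(1.96 × 8.5)² = 277.6`, so 278. Allowing for 10% missing gives `278/0.9 = 309`. The stated figure of up to 500 is not reproduced from these inputs. Because it is a ceiling, this does not affect the point here, and 500 is used below.

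**Step 1: what the factor becomes.** Let a fraction f be missing in every country, so `n_h = (1 − f)N_h`, and let `n = 500(1 − f)`. Then

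- as written: `V = Σ (N_h/N)² × f/n_h × s² = f s²/n`
- without the factor: `V = Σ (N_h/N)² × s²/n_h = s²/n`

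The written standard error is therefore √f times the correct one, whatever the split between countries.

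**Step 2: after the planned imputation.** Every patient has a value, so `n_h = N_h`, `N_h − n_h = 0` and `V = 0`. The half-width is 0 for any SD, sample size or country split. The correct half-width with 500 fully observed patients would be `1.96 × 8.5/√500 = 0.75`.

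**Step 3: missing values left out.** Half-widths are `1.96 × 8.5 × √(f/n)` as written and `1.96 × 8.5/√n` corrected. True coverage of the written interval is `2Φ(1.96√f) − 1`.

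| Missing f | n | As written | Correct | Ratio 1/√f | True coverage |
|---|---|---|---|---|---|
| 5% | 475 | 0.17 | 0.76 | 4.47 | 34% |
| 10% (plan) | 450 | 0.25 | 0.79 | 3.16 | 46% |
| 20% | 400 | 0.37 | 0.83 | 2.24 | 62% |
| 27% | 365 | 0.45 | 0.87 | 1.92 | 69% |

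Only the 10% row is the plan's assumption. The 27% row is an illustration: if patients were catheterised, and so not evaluable, at the rate in the historical cohort of section 1 (54 of 286, 18.9%), and 10% of the rest lacked a score, then `1 − 0.811 × 0.9 = 0.27`. It also assumes that `N_h` counts the non-evaluable patients.

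**Step 4: simulation.** In 20,000 runs with normal changes, SD 8.5, countries of 75, 125, 125 and 175 patients and about 90% observed in each, the written interval covered the true mean 46.9% of the time (mean half-width 0.25). The interval without the factor covered it 95.2% of the time (mean half-width 0.78).

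**Step 5: imputation once the factor is gone.** If imputed averages are counted as observed and add no variance, the half-width is about `1.96 × 8.5 × √(449/499)/√500 = 0.71`, against 0.79 from the 450 observed patients. Removing the factor cures most of the problem, but single mean imputation would still understate the uncertainty.

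**The case against.** The strongest reply is that this is a slip of notation. In the same section `S_h²` is summed to `N_h` around a stratum mean `μ_h`, while `s_h²` is summed to `n_h` around the sample mean. That is how a text with population size `N_h` and sample size `n_h` would read. If `N_h` were a large national population, the factor would be close to 1 and the interval essentially right. The sample size supports this: on the literal formula, 10% missing would give ±1 with about `277.6 × 0.1/0.9 = 31` patients, so nobody sizing the trial at up to 500 had that formula in mind.

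This may well explain the error, but it does not rescue the text. The definition says sample size. The documents give no population size for any country, so on the population reading neither the weights nor the variance could be computed. If the populations are large, deleting the factor changes nothing, so both readings lead to the same correction.

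A second reply is that the formula is approximately valid for the mean of the enrolled cohort itself, if data are missing at random. That is true of the analysis without imputation. It does not fit the aim in section 2, and it cannot justify zero width when missing scores have been replaced by averages.

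Third, a zero-width interval would be noticed in programming. Probably so, but a half-width of 0.25 looks plausible and might not be, and a repair made after the data are seen would be post hoc. The general allowance for t-based intervals in section 8.5.1.1 does not help, because section 8.5.1 yields to more specific provisions and section 8.5.2 is one.

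Two limits stand. With missing values left out, the written formula does not meet ±1 in every case: at 500 patients and SD 8.5 it fails beyond about 64% missing (the correct formula fails beyond about 44%). Under the planning assumptions the target is met with either formula, so the error misstates precision and does not reverse whether the objective is met.

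**Conclusion.** The concern holds. As written, the primary 95% interval has zero width after the planned imputation. This is algebra and needs no assumption beyond the plan's own definition of `N_h`. In the analysis without imputation, the interval is about 3.2 times too narrow at the planned 10% missing (0.25 against 0.79), with true coverage of about 46%.

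The second result takes `N_h` as all patients in the stratum and `n_h` as those with observed change scores, with equal missingness across countries. If `N_h` were restricted to patients with data, the width would again be zero. If it also counted patients excluded from the analysis set, the ratio would be smaller but still above 1. Every reading that keeps the stated definition understates the uncertainty. The coverage figures are for the mean in PAE patients beyond those enrolled. The fault lies in the formula and not in the number of patients.

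**What to change.** In section 8.5.2, delete the finite-population factor and the reference to sampling without replacement, and write `V̂ = Σ W_h² s_h²/n_h`. Define `W_h = N_h/N` as the country's share of enrolment in the analysis set and `n_h` as the number of patients in country h with both baseline and 12-month IPSS observed. Print the sample variance `s_h²` in the estimator, where the text now shows `S_h²`.

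In section 8.5.2.1, if imputation is kept for the primary analysis, replace the age-specific average with multiple imputation combined by Rubin's rules, so that imputed values are not counted as observed.

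The cost is one formula and two definitions, plus a short imputation specification if that route is kept. No data collection changes and no extra patients are needed: the corrected half-width is 0.79 with 450 observed patients and 0.75 with 500. The reported interval will be wider than the current formula would give. The change should be made before the 12-month data are analysed.

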### 8.5.2.1 Missing Data

Missing data for the IPSS will be imputed as the age-specific average for that time point. Also, a tipping point analysis will be performed where the analysis will be performed, excluding the missing data. The number of missing data points it takes to tip the results from one direction to the other will be reported.

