## 7 Patient Completion and Discontinuation

Patients will be informed that they have the right to withdraw from the study at any time for any reason, without prejudice to their medical care. The investigator also has the right to withdraw patients from the study for any reason. If a patient is withdrawn or discontinued from the study, the reason for withdrawal from the study will be recorded on the end of study form. These subjects will not be replaced.

A subject will be considered lost to follow-up if he fails to return for more than one scheduled visit and is unable to be contacted by the study site staff.

The following actions must be taken if a subject fails to return for a required study visit:

- The site will attempt to contact the subject and reschedule the missed visit within the allowable visit timeline and counsel the subject on the importance of maintaining the assigned visit schedule and ascertain if the subject wishes to and/or should continue in the study
- Before a subject is deemed lost to follow-up, the Investigator(s) or designees will make every effort to regain contact with the subject (where possible, 3 telephone calls and, if necessary, a certified letter to the subject's last known mailing address or local equivalent methods). These contact attempts must be documented

- Should the subject continue to be unreachable, he or she will be considered to have withdrawn from the study with a primary reason of lost to follow-up

If a patient receives any non-PAE BPH procedure other than biopsy after his study PAE he will be automatically discontinued from the study, and follow-up data will no longer be collected. BPH procedures that will automatically discontinue the patient include but are not limited to TURP, Urolift, microwave ablation, aquablation, laser therapy and non-Embosphere Microspheres PAE.

Patients requiring multiple PAE procedures:

- If a patient receives an additional PAE procedure with Embosphere Microspheres after the initial treatment, he will remain in the study, and the schedule for the follow-up evaluations will begin according to the date of the first PAE with Embosphere Microspheres procedure until the subject reaches a total of 24 months follow-up. End of study will be calculated based on first PAE procedure for 24 months.

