## 8.4 Analysis Populations

### 8.4.1 Full Analysis Set (FAS)

Includes all patients that were enrolled except those that withdrew consent before the index procedure. The FAS is the population that will be used in determining endpoints except for efficacy endpoints

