### 8.4.2 Evaluable Analysis Set (EAS)

Includes FAS patients where there are no significant deviations (e.g. not meeting the inclusion/exclusion criteria) from the protocol that did not have an indwelling catheter at the end of the procedure.

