### **8.5.1.5 Missing Data**

All attempts will be made to limit the amount of missing data. For all analyses of the primary endpoints, the number of observations available will be reported so the reader can assess the impact of missing data. For all clinical endpoints except for the patient-reported outcome measurements, an adjustment to the denominator will be made based on the amount of evaluable data. For each visit (or reporting time point), the event rate will be calculated as the number of subjects with certain event terms over the number of evaluable subjects. The evaluable subjects at each reporting time point include all subjects who are enrolled and

- 1) had an event within (on or before) the reporting cutoff days, or

- 2) had a follow-up at or after the lower limit of the reporting window, or
- 3) the withdrawal consent date/recorded lost-to-follow-up date at or after the lower limit of the reporting window.

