## 8.5.3 Analysis of the Secondary Endpoints

### 8.5.3.1 IPSS changes over time

The changes over time in the IPSS using the EAS will be modeled using a linear mixed model where country and patient will be considered a random effect. If there is evidence of non-linearity, a nonlinear mixed-effects model using a 3rd-degree

 Tibshirani, Robert (1996). "Regression Shrinkage and Selection via the lasso". Journal of the Royal Statistical Society. Series B (methodological). Wiley. 58 (1): 267–88. JSTOR 2346178.

polynomial will be implemented. The predicted curve and 95% confidence interval will be reported. Missing data will not be imputed.

Sensitivity analyses using complete cases and missing values replaced with an age-specific average will be performed.

A multivariate linear model will be developed to predict the IPSS changes over time. Univariate analysis will be performed analyses for all the baseline characteristics. Based on those results combined with clinical judgment, a final set of baseline characteristics will be created for use in the multivariate model. The LASSO regression analysis method will be used to perform variable selection and regularization.

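### Men who have another BPH procedure before their 12-month IPSS are, on the plan's wording, filled with an age average, and no planned IPSS analysis gives them an unfavourable value

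*Combined protocol and SAP*

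**What the plan says.** Section 7 covers a man who, after his study PAE, has a non-PAE BPH procedure other than biopsy, or a PAE with a non-Embosphere product: "he will be automatically discontinued from the study, and follow-up data will no longer be collected". A man with a repeat Embosphere PAE stays in. For anyone withdrawn, "the reason for withdrawal from the study will be recorded on the end of study form".

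The primary endpoint is the 12-month IPSS (Section 8.1.1), analysed as mean change from baseline (Sections 8.2 and 8.5.2). Section 8.5.2.1 sets the rule for gaps: "Missing data for the IPSS will be imputed as the age-specific average for that time point". It adds a tipping-point analysis, described as run without the missing data: "The number of missing data points it takes to tip the results from one direction to the other will be reported".

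The analysis sets do not remove a man for a later procedure. The FAS "Includes all patients that were enrolled except those that withdrew consent before the index procedure"; the EAS "Includes FAS patients where there are no significant deviations" and no catheter at the end of the procedure.

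For IPSS over time, Section 8.5.3.1 plans a mixed model without imputation, and then: "Sensitivity analyses using complete cases and missing values replaced with an age-specific average will be performed". Section 8.5.1.5 promises the number of observations, but its denominator rule passes over the IPSS: "For all clinical endpoints except for the patient-reported outcome measurements, an adjustment to the denominator will be made". Sections 8.1.2 and 8.5.3.5 count treatments for refractory or recurrent LUTS as a separate secondary endpoint.

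**The concern.** A man who goes on to another BPH procedure may well have had less benefit from his PAE than the average man of his age. Under Sections 7 and 8.5.2.1 read together, his missing score becomes that average. The primary result is a single mean change, to be estimated within 1 unit either way, so its accuracy matters as well as its sign. The plan does not say how such a procedure counts in that mean, and it offers no IPSS analysis that would show how far the result depends on the default.

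**Working it through.** The plan states no figure for this effect, so there is none to reproduce.

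**Inputs from the documents**
- Earlier cohort (Section 1): mean IPSS 21.5 at baseline and 6.2 at 9-16 months, so change = 6.2 - 21.5 = -15.3. This is illustrative only; 54 of those 286 men had indwelling catheters at baseline.
- Planned precision (Section 8.3): full interval width 2, half-width 1.
- Allowance for a missing baseline or 12-month IPSS, all causes (Section 8.3): 10%.

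**Assumed, because the documents do not give them**
- p, the share with a discontinuing procedure before the 12-month IPSS: 1, 2, 5 or 10%.
- s, how much less these men improved than the average: 5, 10 or 15.3 points. The last means total loss of benefit and is high.

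**Step 1: size.** Let m be the mean change among men with a score. If the target is the effect of the study PAE, the true mean is (1 - p)m + p(m + s) = m + ps. Age fill reports about m, so the overstatement is p x s.

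| p | s = 5 | s = 10 | s = 15.3 |
|---|---|---|---|
| 1% | 0.05 | 0.10 | 0.15 |
| 2% | 0.10 | 0.20 | 0.31 |
| 5% | 0.25 | 0.50 | 0.77 |
| 10% | 0.50 | 1.00 | 1.53 |

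The 10% row is extreme, since these procedures alone would use the whole missing-data allowance. With total loss of benefit the shift reaches 1 unit at 1/15.3 = 6.5%, about 33 of 500 men. The 1-unit half-width is a measure of random error and is used here only for scale.

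**Step 2: do filled men enter the estimate?** The variance in Section 8.5.2 contains (N_h - n_h)/(N_h n_h). If N_h is the stratum sample and n_h the men with data, filling every gap makes n_h = N_h and the variance zero. That reading gives a usable interval only when missing men are left out. The choice hardly matters here. With 500 men, 25 affected and s = 15.3:
- target: (475 x -15.3 + 25 x 0)/500 = -14.54
- age fill: (475 x -15.3 + 25 x -15.3)/500 = -15.3
- left out: (475 x -15.3)/475 = -15.3

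The last two agree exactly only if affected men match the others on age and baseline IPSS; otherwise they are close.

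**Step 3: the other IPSS analyses.** The complete-case and age-fill sensitivity analyses are the two just compared. The mixed model has only the man's earlier scores. None assigns an unfavourable 12-month value.

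**Step 4: the tipping count.** No values or threshold are named. If tipping means reversal of direction, then with 10% missing it needs 0.9 x (-15.3) + 0.1w = 0, so w = 137.7: the missing men would have to average 137.7 points worse than baseline, nine times the assumed improvement. Such a count cannot reveal a shift of about 1 point.

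**Step 5: what better analyses would show.**
- Setting change = 0 for affected men gives -15.3(1 - p): -15.15, -14.99, -14.54 and -13.77 at 1, 2, 5 and 10%.
- A delta adjustment with 50 of 500 missing, 10 of them after a discontinuing procedure (both assumed), gives -15.3 + (10 x d1 + 40 x d2)/500, where d1 applies to those 10 and d2 to the other 40. Shifts (d1, d2) of (5, 2), (15.3, 2) and (15.3, 5) give -15.04, -14.83 and -14.59.

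**The case against.** **The target may be different.** Section 2 speaks of a real-world setting, which fits a target of the man's status whatever later treatment he has. Age fill need not overstate that, because the later procedure may itself relieve symptoms. This stands. A reader might infer that the primary estimate is shown to be biased; the documents support only a conditional statement. Sections 3.1 and 8.2, which speak of the effectiveness of PAE and the efficacy of the device, point towards the other target, but the plan never says.

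**The rule is inferred.** No single sentence says these men receive the age average, and Section 8.5.2 leaves their place in the estimate unclear. This stands as a limit on wording. It does not remove the concern, because leaving them out has nearly the same effect.

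**They need not all be failures.** A reader might infer that the plan classes all these men as treated for refractory or recurrent LUTS. It does not. Section 7 gives no indication for the discontinuing procedure. The counts in Section 8.5.3.5 are not limited to discontinuing procedures and may include repeat Embosphere PAE. The groups overlap but are not defined as the same.

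**Readers can bound the effect.** Treatment counts and the number of observations are to be reported, and withdrawal reasons are recorded. This stands in part. The bound is rough, and no pre-specified analysis links those counts to the IPSS.

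**A tipping-point analysis is planned.** The term suggests trying worse values, but the text excludes missing data and names none.

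**The effect is small.** At 1-5% with 5-10 points lost it is 0.05 to 0.50 on about 15, in a single-arm study with no success threshold. This stands, and it bears on severity.

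**Conclusion.** The point holds in conditional form and should be fixed. The plan does not state how a discontinuing procedure before month 12 counts in the primary estimate. Its default treats these men as average or leaves them out, and no planned IPSS analysis is specified to treat them less favourably.

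If the target is the effect of the study PAE, improvement is overstated by rate times shortfall: 0.10 to 0.31 points at 2% and 0.25 to 0.77 at 5%, for shortfalls of 5 to 15.3 points. Rate and shortfall are assumptions throughout, and 15.3 borrows the earlier cohort's means. A reader might infer that the bias exceeds the planned precision; that needs about 6.5% of men affected with total loss of benefit, and nothing in the documents establishes either. The conclusion that men improve is not in doubt. What is open is how much of the reported 12-month improvement rests on the default. Confidence is medium.

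**What to change.** In Section 8.5.2.1:

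1. State how a discontinuing procedure before month 12 counts in the primary estimate, and whether men with filled scores enter the Section 8.5.2 formula.
2. Add a pre-specified sensitivity analysis, among men with a baseline IPSS, that sets the 12-month change to 0 for those with such a procedure. Report how many men are affected.
3. Replace the tipping-point text with a delta adjustment that worsens imputed 12-month values in steps, with larger shifts for men missing because of a discontinuing procedure. Report the mean change and confidence interval at each step.

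The cost is SAP wording and a little more analysis. Baseline IPSS, additional procedures and withdrawal reasons are already collected, and no visit is added. The downside is a possibly smaller reported improvement. One caveat: if the sponsor chooses status whatever later treatment is given, Section 7 stops the data that target would need. Wording alone would then leave these men's contribution resting on imputation, and the SAP should say so.

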## **3 Study Objectives**

### **3.1 Primary Objective:**

Evaluate the long-term effectiveness of prostatic artery embolization (PAE) with Embosphere Microspheres as assessed by the International Prostate Symptom Score (IPSS) for those subjects who are eligible to complete a baseline IPSS for comparative purposes.

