## **8 Statistical Considerations**

### **8.1 Endpoint Definitions**

#### **8.1.1 Primary Endpoints**

The primary endpoint is the IPSS at 12 months.

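### Filling each missing IPSS with one age-specific mean makes the primary 95% CI too narrow, and it biases the 12-month change when missingness depends on the 3-month score

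*Combined protocol and SAP*

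**What the plan says.** Section 8.1.1: "The primary endpoint is the IPSS at 12 months". Sections 8.2 and 8.5.2 analyse it as change from baseline, to be estimated within 1 unit either way.

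Section 8.5.2.1, under the primary analysis: "Missing data for the IPSS will be imputed as the age-specific average for that time point". It does not define the age bands or say whether the average comes from this study. It then adds that "a tipping point analysis will be performed where the analysis will be performed, excluding the missing data", which describes a complete-case run.

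Section 8.5.2 builds a z-interval from the within-country sample variance and says its variance estimate "is the unbiased estimator of" the variance of the stratified mean. It has no term for imputed values.

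Section 8.5.3.1 ranks the methods the other way for IPSS over time. The main analysis is a mixed model in which "Missing data will not be imputed", and the run with "missing values replaced with an age-specific average will be performed" is a sensitivity analysis.

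IPSS is collected at baseline, 3, 12 and 24 months (section 4).

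**The concern.** A value filled with a group mean has no residual scatter, yet it counts as a full observation. The variance comes out too small and the sample size too large. No sentence says that filled values are treated as observed, but sections 8.5.2 and 8.5.2.1 offer no other treatment.

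The fill also uses age alone. A man's 3-month IPSS is scheduled and is likely to say more about his 12-month score. If men with poor 3-month scores are more often missing at month 12, they are given the average of men still followed (if the average is the study's own), and the improvement looks larger than it was.

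Outcome-related loss is plausible under this protocol. Section 7 stops data collection after a non-PAE BPH procedure. Section 4 does not require an IPSS from men with an indwelling catheter, and the Evaluable Analysis Set excludes only men with a catheter at the end of the procedure.

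The study's main result is an estimate with a 95% CI, so accuracy and honest error bars are what it has to deliver.

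**Working it through.** **Plan's own figure.** With SD 8.5 and half-width 1 (section 8.3), n = (1.96 × 8.5 / 1)² = 277.6, so 278. Allowing for 10% missing, 278 / 0.9 = 308.9, so 309. The stated inputs do not reproduce 500, and the exact country allocation is not given. With 450 evaluable of 500 the half-width is 1.96 × 8.5 / √450 = 0.785, inside the target. The checks below use N = 500.

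**Inputs.** SD of change 8.5 and 10% missing (section 8.3). Baseline SD 6.8 and 9-16-month SD 5.8, from the prior cohort in section 1; these are not planning values of this study. Combining the two sources is an assumption. It gives covariance (6.8² + 5.8² − 8.5²)/2 = (46.24 + 33.64 − 72.25)/2 = 3.815, a correlation of 3.815/(6.8 × 5.8) = 0.10.

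**CI width.** Assume that a fraction f of 12-month scores is missing completely at random, baseline is observed, there is no age effect, and the variance is the ordinary one.

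- Reported variance = [(1 − f) × 8.5² + f × 6.8²] / N
- Valid variance = 5.8²/[N(1 − f)] + 6.8²/N − 2 × 3.815/N

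At f = 0.10 the reported variance is (65.025 + 4.624)/500 = 0.1393, half-width 0.732. The valid variance is 33.64/450 + 46.24/500 − 7.63/500 = 0.1520, half-width 0.764. Coverage is 2Φ(1.96 × ratio) − 1.

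| Missing | Reported half-width | Valid half-width | Too narrow by | Coverage |
|---|---|---|---|---|
| 10% | 0.732 | 0.764 | 4% | 93.9% |
| 20% | 0.718 | 0.787 | 9% | 92.6% |
| 30% | 0.704 | 0.816 | 14% | 90.9% |

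If the change itself were filled, the figures at 10% missing would be 0.707 against 0.785: 10% too narrow, coverage 92.2%.

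**Bias.** Bias is about f times the gap in true 12-month IPSS between missing and observed men. At f = 0.10, a gap of 5 points gives 0.5 points.

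To size the gap, 500 men were simulated with the SDs above (5.8 also at 3 months), and 12-month missingness was made to depend on the 3-month IPSS. Two inputs are assumptions: a 3-to-12-month correlation of 0.5 to 0.7, and log-odds of missing of 0.5 to 1 per SD of the 3-month score. In the table, men doing badly are the ones missing.

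| Missing | Correlation | Log-odds per SD | Overstated by | Coverage |
|---|---|---|---|---|
| 10% | 0.5 | 0.5 | 0.14 | 92% |
| 10% | 0.6 | 0.5 | 0.18 | 91% |
| 10% | 0.6 | 1 | 0.32 | 84% |
| 10% | 0.7 | 1 | 0.37 | 82% |
| 14.5% | 0.5 | 0.5 | 0.21 | 90% |
| 14.5% | 0.7 | 1 | 0.53 | 70% |

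With the slope reversed, so that men doing well are missing (14.5%, correlation 0.6, log-odds 1), improvement is understated by about 0.44. With missingness unrelated to IPSS the bias is about zero, and only the CI problem remains. A regression on baseline and 3-month IPSS had bias of about 0.02 or less in such scenarios. That is expected, because the data were generated as missing at random given those scores.

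**The case against.** The effect is modest at the planned missingness. Both half-widths at 10% meet the 1-point target, and coverage is near 94% if loss is unrelated to outcome. The prior cohort improved by 21.5 − 6.2 = 15.3 points, so a few tenths would not change the reading. Section 8.5.2.1 also plans a run without the missing data, section 8.5.1.5 requires the number of observations to be reported, and section 8.5.3.1 already holds an un-imputed mixed model. All of this stands, and it limits the size of the point. The complete-case run has a CI of proper width but does not remove the bias. The mixed model is only secondary.

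Stronger readings are tempting and are not supported:

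- A reader might infer that the estimate leans toward benefit whenever missingness depends on earlier scores. It does not: the sign follows who is missing, and no section says which men that will be. If the undefined age-specific average were an external norm, the bias could also run the other way.
- A reader might infer that the plan invents baselines for men exempt from the questionnaire, since section 3.1 limits the objective to an assessment "for those subjects who are eligible to complete a baseline IPSS for comparative purposes". Sections 8.4.1 and 8.4.2 already keep most of these men out of the efficacy set.
- A reader might fault the rule for not using 24-month scores. Section 8.5.6 plans a first report once all men reach the primary endpoint, when many 24-month scores will not yet exist.
- Different methods at one time point are not in themselves a contradiction; sensitivity analyses work that way. The weakness is which method is primary.

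The finite-population factor in section 8.5.2, with stratum size defined as a sample size, is a separate matter and is not counted in these figures.

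**Conclusion.** The point holds. As written, the primary CI is too narrow. At the planned 10% missing it is about 4% too narrow when only 12-month scores are filled, rising to about 14% at 30%. This part needs no outcome-related missingness. It rests on the ordinary variance, the prior-cohort SDs and the inference that filled values count as observed.

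The bias is conditional. If men doing badly at 3 months are the ones missing, improvement is overstated by about 0.14 to 0.37 points at 10% missing (coverage 92% to 82%) and by 0.21 to 0.53 points at 14.5% (coverage 90% to 70%). These ranges depend on the assumed correlations and slopes. An overstatement of 0.37 is about half of the reported half-width of 0.73. That does not threaten a conclusion of large improvement, but it is material to a study whose aim is a precise estimate.

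**What to change.** Replace the first sentence of section 8.5.2.1 with one of these:

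- Estimate the primary 12-month change from a repeated-measures model on observed baseline, 3-month and 12-month IPSS in the efficacy set. Treat visit as categorical, with an unstructured covariance and country and age as fixed effects. Report the 12-month minus baseline contrast at the country shares of section 8.5.2.
- Or use multiple imputation from age, country and the man's other IPSS scores at those visits, combined by Rubin's rules.

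Keep 24-month scores out of the primary estimate so that it does not change between the two reports. Keep the age-mean fill only as a labelled sensitivity analysis, as section 8.5.3.1 already does, and define its age bands and the source of the average.

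The cost is SAP wording, a little programming and a slightly wider CI. No new data are needed. Both options assume missing at random, so neither settles by itself how men discontinued after another BPH procedure are counted. The SAP should state that separately.
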